### *General Medical Exclusion Criteria*

- Women only: pregnancy or lactation
- Evidence of significant uncontrolled concomitant disease that in the opinion of the investigator could affect compliance with the protocol or interpretation of results, including significant liver disease (such as cirrhosis, uncontrolled major seizure disorder, or superior vena cava syndrome)
- Significant cardiovascular disease, such as New York Heart Association (NYHA) cardiac disease (Class II or greater), myocardial infarction within 3 months prior to randomization, unstable arrhythmias, or unstable angina. Patients with a known left ventricular ejection fraction (LVEF) < 40% will be excluded. Patients with known coronary artery disease, congestive heart failure not meeting the above criteria, or LVEF < 50% must be on a stable medical regimen that is optimized in the opinion of the treating physician, in consultation with a cardiologist if appropriate.
- Severe infection requiring systemic treatment within 4 weeks prior to randomization, including but not limited to hospitalization for complications of infection, bacteremia, or severe pneumonia
- Major surgical procedure within 4 weeks prior to randomization or anticipation of the need for a major surgical procedure during the course of the study other than for diagnosis. Placement of central venous access catheter(s) (e.g., port or similar) is not considered a major surgical procedure and is therefore permitted.
- History of severe reactions (e.g. allergic, anaphylactic, or other hypersensitivity) to chimeric or humanized antibodies or fusion proteins
- Known hypersensitivity or allergy to biopharmaceuticals produced in Chinese hamster ovary cells or any component of the atezolizumab formulation
- History of autoimmune disease, including but not limited to myasthenia gravis, myositis, autoimmune hepatitis, systemic lupus erythematosus, rheumatoid arthritis, inflammatory bowel disease, vascular thrombosis associated with antiphospholipid syndrome, Wegener's granulomatosis, Sjögren's syndrome, Guillain-Barré syndrome, multiple sclerosis, vasculitis, or glomerulonephritis. Patients with a history of autoimmune-related hypothyroidism on a stable dose of thyroid replacement hormone are eligible for this study. Patients with controlled Type 1 diabetes mellitus on a stable insulin regimen are eligible for this study.

- Prior allogeneic stem cell or solid organ transplantation

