## 9. EXPECTED TOXICITIES AND DOSING DELAYS/DOSE MODIFICATIONS

### 9.1 Anticipated Toxicities of atezolizumab (Atezolizumab) and Dose Modifications

Toxicities associated or possibly associated with atezolizumab treatment should be managed according to standard medical practice. Additional tests, such as autoimmune serology or biopsies, should be used to evaluate for a possible immunogenic etiology, when clinically indicated. Although most immune-mediated adverse events observed with atezolizumab have been mild and self-limiting, such events should be recognized early and treated promptly to avoid potential major complications. Discontinuation of atezolizumab may not have an immediate therapeutic effect, and in severe cases, immune-mediated toxicities may require acute management with topical corticosteroids, systemic corticosteroids, or other immunosuppressive agents.

The investigator should consider the benefit–risk balance for a given patient prior to further administration of atezolizumab. In patients who have met the criteria for permanent discontinuation, resumption of atezolizumab may be considered if the patient is deriving benefit and has fully recovered from the immune-mediated event. Patients can be re-challenged with atezolizumab only after approval has been documented by both the investigator (or an appropriate delegate) and the Medical Monitor. Guidelines for managing patients who experience selected adverse events are provided in the following sections. Management guidelines are presented by adverse event severity based on the National Cancer Institute (NCI) Common Terminology Criteria for Adverse Events (CTCAE) and in some instances may vary by CTCAE version (4.0 vs. 5.0).

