#### Dose Modification Guidelines for Dermatologic Events

Event	Management
Dermatologic event, Grade 1	
 
Continue atezolizumab.
 
Consider treatment with topical corticosteroids and/or other symptomatic therapy (e.g. antihistamines).
 

Dermatologic event, Grade 2	
 
Continue atezolizumab.
 
Consider patient referral to dermatologist.
 
Initiate treatment with topical corticosteroids.
 
Consider treatment with higher-potency topical corticosteroids if event does not improve.
 
Initiate treatment with higher-potency topical corticosteroids if event does not improve.
 

Dermatologic event, Grade 3	
 
Withhold atezolizumab for up to 12 weeks after event onset.a
 
Refer patient to dermatologist.
 
Initiate treatment with corticosteroids equivalent to 10mg/day oral prednisone, increasing dose to 1-2 mg/kg/day if event does not improve within 48-72 hours.
 
If event resolves to Grade 1 or better, resume atezolizumab.b
 
If event does not resolved to Grade 1 or better while withholding atezolizumab, permanently discontinue atezolizumab and contact Study Chair.c
 

Dermatologic event, Grade 4	
 
Permanently discontinue atezolizumab and contact Study Chair.c
 

a Atezolizumab may be withheld for a longer period of time (i.e., > 12 weeks after event onset) to allow for corticosteroids (if initiated) to be reduced to the equivalent of ≤ 10 mg/day oral prednisone. The acceptable length of the extended period of time must be agreed upon by the investigator and the Stud Chair.

b If corticosteroids have been initiated, they must be tapered over ≥ 1 month to the equivalent of ≤ 10 mg/day oral prednisone before atezolizumab can be resumed.

c Resumption of atezolizumab may be considered in patients who are deriving benefit and have fully recovered from the immune-mediated event. Patients can be re- challenged with atezolizumab only after approval has been documented by both the investigator (or an appropriate delegate) and the Study Chair.

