**Management Guidelines for Endocrine Events (cont.)**

Event	Management
Symptomatic adrenal insufficiency, Grade 2-4	
 
• Withhold atezolizumab for up to 12 weeks after event onset. a
 
• Refer patient to endocrinologist.
 
• Perform appropriate imaging.
 
• Initiate treatment with corticosteroids equivalent to 1-2 mg/kg/day IV methylprednisolone and convert to 1-2 mg/kg/day oral prednisone or equivalent upon improvement.
 
• If event resolves to Grade 1 or better and patient is stable on replacement therapy, resume atezolizumab.b
 
• If event does not resolve to Grade 1 or better or patient is not stable on replacement therapy while withholding atezolizumab, permanently discontinue atezolizumab and contact Study Chair.c
 

Hyperglycemia, Grade 1 or 2	
 
• Continue atezolizumab.
 
• Investigate for diabetes. If patient has Type 1 diabetes, treat as a Grade 3 event. If patient does not have Type 1 diabetes, treat as per institutional guidelines.
 
• Monitor for glucose control.
 

Hyperglycemia, Grade 3 or 4	
 
• Withhold atezolizumab.
 
• Initiate treatment with insulin.
 
• Monitor for glucose control.
 
• Resume atezolizumab when symptoms resolve and glucose levels are stable.
 

Hypophysitis (pan-hypopituitarism), Grade 2 or 3	
 
• Withhold atezolizumab for up to 12 weeks after event onset. a
 
• Refer patient to endocrinologist.
 
• Perform brain MRI (pituitary protocol).
 
• Initiate treatment with corticosteroids equivalent to 1-2 mg/kg/day IV methylprednisolone and convert to 1-2 mg/kg/day oral prednisone or equivalent upon improvement.
 
• Initiate hormone replacement if clinically indicated.
 
• If event resolves to Grade 1 or better, resume atezolizumab.b
 

	
 
• If event does not resolve to Grade 1 or better while withholding atezolizumab, permanently discontinue atezolizumab and contact Study Chair. c
 
• For recurrent hypophysitis, treat as a Grade 4 event.
 

--	--

MRI=magnetic resonance imaging; TSH = thyroid-stimulating hormone.

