### 9.2.7 Potential Eye Toxicity

An ophthalmologist should evaluate visual complaints. Uveitis or episcleritis may be treated with topical corticosteroid eye drops. Atezolizumab should be permanently discontinued for immune-mediated ocular disease that is unresponsive to local immunosuppressive therapy.

Potential eye toxicity should be managed according to the guidelines in the table below.

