#### Management Guidelines for Ocular Events

Event	Management
Ocular event, Grade 1	
 
• Continue atezolizumab.
 
• Patient referral to ophthalmologist is strongly recommended.
 
• Initiate treatment with topical corticosteroid eye drops and topical immunosuppressive therapy.
 
• If symptoms persist, treat as a Grade 2 event.
 

Ocular event, Grade 2	
 
• Withhold atezolizumab for up to 12 weeks after event onset.a
 
• Patient referral to ophthalmologist is strongly recommended.
 
• Initiate treatment with topical corticosteroid eye drops and topical immunosuppressive therapy.
 
• If event resolves to Grade 1 or better, resume atezolizumab.b
 
• If event does not resolve to Grade 1 or better while withholding atezolizumab, permanently discontinue atezolizumab and contact Study Chair.c
 

Ocular event, Grade 3 or 4	
 
• Permanently discontinue atezolizumab and contact Study Chair.c
 
• Refer patient to ophthalmologist.
 
• Initiate treatment with corticosteroids equivalent to 1-2 mg/kg/day oral prednisone.
 
• If event resolves to Grade 1 or better, taper corticosteroids over <math>\geq 1</math> month.
 

a Atezolizumab may be withheld for a longer period of time (i.e., > 12 weeks after event onset) to allow for corticosteroids (if initiated) to be reduced to the equivalent of  $\leq 10$  mg/day oral prednisone. The acceptable length of the extended period of time must be agreed upon by the investigator and the Study Chair.

b If corticosteroids have been initiated, they must be tapered over  $\geq 1$  month to the equivalent of  $\leq 10$  mg/day oral prednisone before atezolizumab can be resumed.

c Resumption of atezolizumab may be considered in patients who are deriving benefit and have fully recovered from the immune-related event. Patients can be re-challenged with atezolizumab only after approval has been documented by both the investigator (or an appropriate delegate) and the Study Chair.

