### **Management guidelines for SCARs**

- For suspected SCARs the patients should be referred to a dermatologist for further diagnosis and management
- Atezolizumab should be withheld for patients with suspected SJS or TEN
- Atezolizumab should be permanently withdrawn for any grade confirmed SJS or TEN
- Caution should be used when considering the use of atezolizumab in a patient who has previously experienced a severe or life-threatening skin adverse reaction on prior treatment with other immune-stimulatory anticancer agents

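### Atezolizumab stop rules conflict for an ocular event that stays at Grade 1 on topical therapy and for confirmed SJS/TEN, and two different re-challenge approvers are named

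*Combined protocol and SAP*

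**What the plan says.** **Ocular events (Section 9.2.7 and its table).** The text says: "Atezolizumab should be permanently discontinued for immune-mediated ocular disease that is unresponsive to local immunosuppressive therapy". It then says: "Potential eye toxicity should be managed according to the guidelines in the table below". In the table, a Grade 1 event continues on atezolizumab with topical steroid drops and topical immunosuppressive therapy, followed by: "If symptoms persist, treat as a Grade 2 event". The Grade 2 row withholds atezolizumab for up to 12 weeks, gives topical therapy again, resumes at Grade 1 or better, and discontinues permanently if that level is not reached. Grades 3 and 4 are a permanent stop.

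**SJS/TEN (Sections 9.2.13, 9.2.3 and 9.1).** The guidelines for severe cutaneous adverse reactions (SCARs) say: "Atezolizumab should be permanently withdrawn for any grade confirmed SJS or TEN". The dermatologic table in Section 9.2.3 continues atezolizumab at Grades 1 and 2. At Grade 3 it withholds the drug and then says: "If event resolves to Grade 1 or better, resume atezolizumab". Grade 4 is a permanent stop, but its footnote c lets resumption be considered after full recovery. Section 9.1 has a general clause to the same effect: "In patients who have met the criteria for permanent discontinuation, resumption of atezolizumab may be considered if the patient is deriving benefit".

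**Who approves re-challenge.** Section 9.1 requires documented approval by the investigator and the Medical Monitor. The footnotes to the ocular and dermatologic tables require the investigator and the Study Chair.

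**The concern.** Section 9 decides, event by event, whether a patient stays on the test drug. If two entries in it give different answers for the same patient, a site cannot comply with both, and two sites can treat the same event differently while each follows the protocol.

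The ocular conflict is between a permanent stop and a hold followed by routine resumption that needs no approval. The SJS/TEN conflict is between a permanent stop at any grade and a table that continues or resumes by grade, with a general clause that leaves re-exposure open. Section 9.2.13 itself describes these skin reactions as potentially fatal, so the issue is patient safety first. For the data, the effect is that reasons for stopping atezolizumab would not mean the same thing at every site.

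**Working it through.** No formula applies to the conflict itself, so each case is traced through the text, the table row and the footnotes.

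**1. Immune-mediated ocular event that stays at Grade 1**

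- Start: Grade 1, topical therapy given, atezolizumab continues.
- The symptoms persist at Grade 1. Under the text of Section 9.2.7 the event has not responded to local therapy, so atezolizumab stops permanently.
- Under the table the event is handled as Grade 2, so atezolizumab is withheld for up to 12 weeks.
- The Grade 2 row resumes at Grade 1 or better. This event meets that condition on the day the hold begins.
- The Grade 2 row stops permanently only if Grade 1 is not reached. That cannot happen unless the event worsens.

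So while the event remains at Grade 1, the table never arrives at the stop that the text requires. At other grades there is no conflict: an unresolved Grade 2 event and any Grade 3 or 4 event lead to permanent discontinuation in the table, which agrees with the text.

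**2. Confirmed SJS/TEN**

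Section 9.2.3 applies its table to dermatologic toxicity and rash in general. Section 9.2.13 describes SCARs as immunologically mediated skin eruptions, so on the plain wording both sections cover the same event.

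| Grade | Section 9.2.13 | Section 9.2.3 table |
|---|---|---|
| 1 or 2 | permanent withdrawal | continue |
| 3 | permanent withdrawal | withhold, resume at Grade 1 or better |
| 4 | permanent withdrawal | permanent stop; re-challenge may be considered (footnote c) |

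Neither section refers to the other. Section 9.2.13 carries no re-challenge footnote. The Section 9.1 clause covers patients who met criteria for permanent discontinuation and makes no exception, so whether it reaches a withdrawal under Section 9.2.13 is undetermined.

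**3. Size**

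Section 9.2.13 gives pooled SCAR rates, regardless of severity, of 0.6% for combination therapy and 0.7% for monotherapy. Section 17.2 gives 53 patients per arm.

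- Expected SCARs in the combination arm: 0.006 × 53 = 0.318, about 0.32.
- Chance of at least one: 1 − 0.994^53 = 0.27.
- Control patients may cross over to atezolizumab. The documents do not say how many will. If none do, the total stays at 0.32. If all 53 did, the monotherapy rate would add 0.007 × 53 = 0.37, for a total of 0.32 + 0.37 = 0.69.

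These figures count every SCAR, including erythema multiforme, acute generalised exanthematous pustulosis and DRESS. Section 9.2.13 also reports that only 36 of 99 SCAR cases in the company database were confirmed by histopathology or a specialist. The documents give no SJS/TEN rate for the drug, so the figures are upper bounds for confirmed SJS/TEN. No frequency is given for persistent Grade 1 ocular events.

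**The case against.** **The ocular table can be read as a sequence.** The text itself hands management to the table. On this view a Grade 1 event that persists after first treatment is not yet unresponsive: it moves to the Grade 2 row, gets topical therapy again, and is stopped permanently if that fails. This reading is sensible for an event that rises to Grade 2 and does not come down. It does not rescue the event that stays at Grade 1, because failure in the Grade 2 row means not reaching Grade 1. The text sets no Grade 1 exception.

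**The specific rule should prevail over the general one.** Section 9.2.13 is a dedicated section, expressly covers any grade, and carries no re-challenge footnote. Section 9.2.3 is introduced by a description of mostly mild, self-limited rash. Most clinicians would follow Section 9.2.13. This is the natural reading, but the protocol does not state it. It also does not settle whether the Section 9.1 clause applies after such a withdrawal.

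**A reader might infer that the protocol tells sites to resume after any SJS/TEN stop.** It does not. Re-challenge is permissive, requires full recovery and needs two documented approvals. Only the Grade 3 dermatologic row words resumption as an instruction.

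**A reader might also infer a third contradiction, on Type 1 diabetes.** Section 5.2 says: "Patients with controlled Type 1 diabetes mellitus on a stable insulin regimen are eligible for this study". The hyperglycemia row for Grades 1 and 2 continues atezolizumab but adds: "If patient has Type 1 diabetes, treat as a Grade 3 event". That is one path, a default with a stated exception, leading to a temporary hold with its own resume criterion. Eligibility at entry is not an instruction to continue treatment. Nor is it clear that a patient's usual glucose would trigger the row. Section 13.5.4 treats a pre-existing condition as an adverse event only if it worsens, and Section 13.3.1 limits when a laboratory value counts as one. What remains is that the row does not say whether it covers pre-existing disease.

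**Conclusion.** Two stop rules conflict as written: the ocular text against its table, for an immune-mediated event that stays at Grade 1 despite topical therapy; and Section 9.2.13 against the dermatologic table and the Section 9.1 clause, for confirmed SJS/TEN. The mismatch between Medical Monitor and Study Chair is a separate, smaller discrepancy, but it bears on every re-challenge decision.

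The ocular conclusion rests on reading persistence of symptoms on topical therapy as lack of response to it. It does not extend to persistent ocular events in general. The SJS/TEN conclusion rests on SJS/TEN falling within dermatologic toxicity, which the protocol's own description supports. The Type 1 diabetes wording is at most an ambiguity and is not part of the finding.

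The number affected is small: at most about 0.32 expected SJS/TEN cases in the combination arm, assuming the pooled all-SCAR rate carries over to this trial. The reason to act is the seriousness of the event, not its frequency. The primary PFS comparison is unaffected in sample size, power and type I error.

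**What to change.** The sponsor should make these wording changes and choose the clinical rule in each case:

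- Reconcile the permanent-stop sentence in Section 9.2.7 with the Grade 1 and Grade 2 rows of the ocular table, so that one instruction applies to an event that stays at Grade 1 on topical therapy.
- State whether Section 9.2.13 or Section 9.2.3 governs confirmed SJS/TEN, with a cross-reference between them, and state whether the re-challenge clause in Section 9.1 and footnote c apply after such a withdrawal.
- Name the same re-challenge approver in Section 9.1 and in all table footnotes.
- Optionally, state whether the Type 1 diabetes branch of the hyperglycemia row covers pre-existing disease.

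The cost is edits to a few text and table entries within an amendment. No new procedures or data collection are needed, and Section 17 does not change.

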#### Management Guidelines for Ocular Events

Event	Management
Ocular event, Grade 1	
 
• Continue atezolizumab.
 
• Patient referral to ophthalmologist is strongly recommended.
 
• Initiate treatment with topical corticosteroid eye drops and topical immunosuppressive therapy.
 
• If symptoms persist, treat as a Grade 2 event.
 

Ocular event, Grade 2	
 
• Withhold atezolizumab for up to 12 weeks after event onset.a
 
• Patient referral to ophthalmologist is strongly recommended.
 
• Initiate treatment with topical corticosteroid eye drops and topical immunosuppressive therapy.
 
• If event resolves to Grade 1 or better, resume atezolizumab.b
 
• If event does not resolve to Grade 1 or better while withholding atezolizumab, permanently discontinue atezolizumab and contact Study Chair.c
 

Ocular event, Grade 3 or 4	
 
• Permanently discontinue atezolizumab and contact Study Chair.c
 
• Refer patient to ophthalmologist.
 
• Initiate treatment with corticosteroids equivalent to 1-2 mg/kg/day oral prednisone.
 
• If event resolves to Grade 1 or better, taper corticosteroids over <math>\geq 1</math> month.
 

a Atezolizumab may be withheld for a longer period of time (i.e., > 12 weeks after event onset) to allow for corticosteroids (if initiated) to be reduced to the equivalent of  $\leq 10$  mg/day oral prednisone. The acceptable length of the extended period of time must be agreed upon by the investigator and the Study Chair.

b If corticosteroids have been initiated, they must be tapered over  $\geq 1$  month to the equivalent of  $\leq 10$  mg/day oral prednisone before atezolizumab can be resumed.

c Resumption of atezolizumab may be considered in patients who are deriving benefit and have fully recovered from the immune-related event. Patients can be re-challenged with atezolizumab only after approval has been documented by both the investigator (or an appropriate delegate) and the Study Chair.

### 9.2.8 Immune-mediated Myocarditis

Immune-mediated myocarditis has been associated with the administration of atezolizumab. Immune-mediated myocarditis should be suspected in any patient presenting with signs or symptoms suggestive of myocarditis, including, but not limited to, laboratory (e.g., BNP [B-Natriuretic Peptide]) or cardiac imaging abnormalities, dyspnea, chest pain, palpitations, fatigue, decreased exercise tolerance, or syncope.

Immune-mediated myocarditis needs to be distinguished from myocarditis resulting from infection (commonly viral, e.g., in a patient who reports a recent history of gastrointestinal illness), ischemic events, underlying arrhythmias, exacerbation of preexisting cardiac conditions, or progression of malignancy.

All patients with possible myocarditis should be urgently evaluated by performing cardiac enzyme assessment, an ECG, a chest X-ray, an echocardiogram, and a cardiac MRI as appropriate per institutional guidelines. A cardiologist should be consulted. An endomyocardial biopsy may be considered to enable a definitive diagnosis and appropriate treatment, if clinically indicated.

Patients with signs and symptoms of myocarditis, in the absence of an identified alternate etiology, should be treated according to the guidelines provided below.

